5.11 Prior medication and Concomitant medication

Prior medication is defined as any medications start before the date of the first dose of IP.

Concomitant medication is defined as any medications that start before, on, or after the first dose of IP and continue into the treatment period.

6 ANALYSIS POPULATIONS

6.1 Primary Analysis Set

The primary analysis set will include enrolled subjects with baseline and follow-up (Week 48/ET) bone biopsy data.

6.2 Full Analysis Set

The full analysis set for efficacy is defined as all enrolled subjects who receive at least one dose of study drug. This analysis set will be used for the analyses of efficacy endpoints.

6.3 Safety Analysis Set

The safety analysis set consists of all enrolled subjects who receive at least one dose of study drug. This analysis set will be used for the analyses of all safety endpoints.

6.4 Treatment Extension Analysis Set

The treatment extension analysis set consists of all enrolled subjects who continued after the Open-Label Treatment Period and received at least one dose during the Treatment Extension Period. This analysis set will be used for the analyses of efficacy and safety endpoints after Week 48 analysis in addition to the full analysis set and safety analysis set.

6.5 Pharmacokinetics Analysis Set

The pharmacokinetics (PK) analysis set is the subset of subjects in the Safety analysis set who have at least 1 evaluable KRN23 concentration. The PK analysis set will be used for the analysis of the PK endpoints at each specific analysis milestone.

7 DATA SCREENING AND ACCEPTANCE

7.1 Handling of Missing and Incomplete Data

Missing clinical outcome data can occur for multiple reasons, including missed subject visits and measures with missing item scores. Missing and incomplete data will be identified through a review of tables and listings for this study. Missing and incomplete data will be identified for investigation, and possible resolution, by Data Management prior to the study database lock.

For all analyses, missing data will be treated as missing, unless otherwise specified. When a change from baseline is assessed, only subjects with a baseline and at least one post-baseline measurement will be included in the analysis.

7.1.1 Non-Responder Imputation

If no serum data is available to evaluate the key secondary endpoint, the subject will be considered as not achieving a serum phosphorus level above the LLN.

7.1.2 Missing Date Information for Adverse Events and Concomitant Medications

The following conventions will be used to impute missing portions of dates for adverse events and concomitant medications.

Missing Start Dates

- If the day is unknown, then:
 - If the month and year match the first dose of IP start date month and year in this study, then impute the day of the first dose date.
 - Otherwise, assign the first day of the month.
- If the month is unknown, then:
 - If the year matches the year of the first dose of investigational product date in this study, then impute the month and day of the first dose date in this study.
 - Otherwise, assign 'January'
- If the year is unknown, then the date will not be imputed and will be assigned a missing value.

Missing Stop Dates

- If the day is unknown, then assign the last day of the month.
- If the month is unknown, then assign 'December.'
- If the year is unknown, then the date will not be imputed and will be assigned a missing value.

- If the resulting end date is after the date of study completion / discontinuation, set the imputed end date as the date of study completion / discontinuation.

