#### **7.6.5 Safety Analyses**

Safety will be evaluated by the incidence, frequency and severity of AEs and SAEs, including clinically significant changes from baseline to scheduled time points in vital signs and weight, physical examinations, eGFR, chemistry, hematology, urinalysis, immunogenicity, and concomitant medications. Additional safety parameters to assess the risk of ectopic mineralization include renal ultrasound, ECHO and ECG findings. Safety analysis will be performed using the safety analysis set.

All AEs will be coded using the Medical Dictionary for Regulatory Activities (MedDRA). The incidence and frequency of AEs will be summarized by System Organ Class, Preferred Term, relationship to study drug, and severity. All reported AEs with onset during the treatment (i.e. treatment-emergent AEs) will be included in the analysis. For each AE, the percentage of subjects who experienced at least 1 occurrence of the given event will be summarized. Special attention will be given to those subjects who died, discontinued treatment due to an AE, or experienced a SAE (e.g. summaries, listings, and narrative preparation may be provided, as appropriate).

Clinical laboratory data will be summarized by the type of laboratory test. Reference ranges and markedly abnormal results (specified in the SAP) will be used in the summary of laboratory data. The frequency and percentage of subjects who experience abnormal clinical laboratory results (i.e. outside of reference ranges) and/or clinically significant abnormalities

(as determined by the investigator) will be presented for each clinical laboratory measurement.

The SAP will provide additional details on the planned safety analyses.

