8.8.2 Adverse Events

Reported adverse event (AE) terms are coded to MedDRA (version 18.1). All reported events will appear in AE listings, however only TEAEs will be summarized. TEAEs are defined as AEs occurring or worsened in severity on or after the first dose date of IP.

The following AEs will be summarized at each milestone analysis:

- All TEAEs
- Related TEAEs
- TEAE by severity
- Events to monitor:
 - Injection site reactions
 - Immunogenicity
 - Hyperphosphataemia
 - Ectopic mineralization
 - Restless legs syndrome
- Grade 3/4 TEAEs
- Serious TEAEs
- Serious related TEAEs
- TEAEs resulting in discontinuation
- Fatal TEAEs.

The incidence and frequency of AEs will be summarized by System Organ Class (SOC), Preferred Term (PT). Events to monitor will be summarized by PT. Injection site reactions (ISR) will be listed for PT, seriousness, severity, outcome, relationship to study drug, and onset time from IP administration.

Listings will be created for AEs which lead to death, discontinuation of treatment, and SAEs.

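### SAP 7.1.2 can impute a start date later than a known pre-dose stop date, which drops a medication from both summaries and can make an ended AE look treatment-emergent

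*SAP*

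**What the plan says.** SAP 7.1.2 has two start-date rules that lead to the first dose date. If only the day is missing and the month and year are those of the first dose, "then impute the day of the first dose date". If the month is missing and the year is that of the first dose, "then impute the month and day of the first dose date in this study". The section contains one plausibility bound, and it concerns stop dates: "If the resulting end date is after the date of study completion / discontinuation, set the imputed end date as the date of study completion / discontinuation". No rule compares an imputed start with the recorded stop.

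Three definitions use these dates:

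- SAP 5.11: "Prior medication is defined as any medications start before the date of the first dose of IP". A concomitant medication, by contrast, has to carry on into the treatment period, whenever it began.
- SAP 8.8.2: "TEAEs are defined as AEs occurring or worsened in severity on or after the first dose date of IP". The same section adds: "All reported events will appear in AE listings, however only TEAEs will be summarized".
- Protocol 7.6.5 describes treatment emergence by onset: "All reported AEs with onset during the treatment (i.e. treatment-emergent AEs) will be included in the analysis".

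**The concern.** Setting an unknown start to the first dose date is a cautious convention when nothing else is known about timing. It goes wrong when the stop date already settles the matter. An episode that ended before dosing must have started before dosing, yet the rule gives it a start on the dosing day.

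Such records can exist. AEs are collected from informed consent (protocol 7.5.3.11). Screening to Baseline is planned to last up to 31 days (protocol 7.5), and two antibiotic labelling courses fall in that time. Medications are recorded back to 30 days before Screening (protocol 7.5.3.10.3), so medications that stopped before the first dose will be in the database.

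At stake are the prior and concomitant medication tables and, depending on how treatment emergence is derived, the AE tables. Under SAP 7.1.3, an AE taken to have started on or after first dose and lacking a causality entry is also counted as related.

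**Working it through.** The plan gives no figure to reproduce. The check applies the rules literally.

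**Notation.** F = first dose date, S = imputed start, E = recorded stop. Prior: S < F. Concomitant: E on or after F, or ongoing. Treatment-emergent, if derived from imputed onset: S on or after F.

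**General argument.** When either first-dose rule fires, S = F. If E < F, then:

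1. S = F > E, so the start is after the stop.
2. S < F is false, so a medication is not prior.
3. E < F, so a medication is not concomitant. With step 2, it is in neither table.
4. S = F satisfies S on or after F, so an AE is treatment-emergent on an onset derivation.

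**Example with the day unknown (AE or medication).** F = 20 March 2016, start recorded as March 2016, E = 10 March 2016. The imputed start is 20 March, 10 days after the stop. With a true start of, say, 5 March, the medication would be prior and the AE would not be treatment-emergent. Under the rule the medication is in neither table and the AE has an onset on the dosing day.

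**Example with the month unknown (medication).** F = 15 March 2016, start recorded as 2016 only, E = 20 January 2016. The imputed start is 15 March, which is 11 + 29 + 15 = 55 days after the stop. The medication is in neither table.

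**Partial stop dates.** A stop known only to a month before the first-dose month gives the same result. SAP 7.1.2 sets it to the last day of that month, which is still before F.

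**Enumeration.** The rules were applied to every first-dose date in 2016 (an assumed year) crossed with every episode that started and stopped 1 to 31 days before it: 366 × (31 × 32 / 2) = 366 × 496 = 181,536 combinations, with the stop kept known.

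| Missing part of start | First-dose rule fires | Of these: start after stop, in neither medication table, onset on or after F |
|---|---|---|
| Day | 56,760 (31.3%) | 56,760 (100%) |
| Month and day | 171,120 (94.3%) | 171,120 (100%) |

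The 31.3% and 94.3% depend on the uniform grid of dates and do not estimate anything in this trial. The 100% follows from the argument above and does not depend on the grid.

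**The remedy by the same argument.** If the imputed start is required to be no later than E, then S ≤ E < F. The medication is prior, the AE is not treatment-emergent, and no start follows its stop.

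**The case against.** **The SAP does not force the AE consequence.** A reader might infer that every AE that ended before dosing becomes a TEAE. SAP 8.8.2 speaks of AEs *occurring* or worsening on or after the first dose date, not of an imputed start date. SAP section 1 gives the SAP priority over the protocol on statistical matters. A programmer could properly exclude an AE whose stop precedes dosing. This stands: the AE consequence is conditional on an onset-based derivation.

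**The medication rule may not reach prior medications.** The heading of 7.1.2 names adverse events and concomitant medications, and a drug that stopped before dosing is not concomitant under 5.11. On that reading the drug escapes the rule, but the SAP then has no start-date convention for it. If the section covers every recorded medication, the gap is as described. The scope needs stating either way.

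**The convention is conservative.** That is true when the stop is missing or falls on or after first dose, and there the rule should stay. It is not conservative for a medication that disappears from both tables.

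**The records will be few and visible.** AEs are asked about at each visit, SAP 7.1 sends incomplete data to Data Management before lock, and all events appear in listings. This stands as mitigation, but SAP 7.1 offers only possible resolution and gives no ordering rule.

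**Size can be overstated.** A reader might carry the 15 March example over to AEs. On the planned 31-day window, taking Day 0 as Baseline, consent would be no earlier than about 13 February 2016, so an AE that ended on 20 January would not be in the AE data. A reader might also take 1/14 = 7.1% as an expected effect. It is only the weight of one subject in any incidence among 14 and says nothing about how often the problem arises.

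**Conclusion.** The gap is real and minor. Applied literally, SAP 7.1.2 produces a start after the stop whenever a partial start date matches the first dose and the stop is known to precede it. Given that 7.1.2 is applied to all recorded medications, such a medication is lost from both the prior and the concomitant summaries. Given that treatment emergence is derived from imputed onset, such an AE is wrongly tabulated as treatment-emergent; the SAP wording permits that derivation but does not require it.

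The number of affected records is unknown and probably small. The primary OV/BV analysis and the serum phosphorus analyses are untouched, and SAP 8.8 plans no hypothesis testing on safety data.

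**What to change.** Add to SAP 7.1.2, stated to apply to AEs and to all prior and concomitant medications: if the complete or partial stop date shows that the episode ended before the first dose, the first-dose imputation is not used. The start is then imputed as the earliest date consistent with the recorded parts, never later than the stop date and, for AEs, no earlier than informed consent. The AE is then not treatment-emergent and the medication is classed as prior.

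The consent floor is needed because a year-only AE start would otherwise become 1 January, which can precede the period in which AEs are collected. The existing convention stays in force for every other partial date.

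The cost is one SAP sentence and one programming check, with no new data collection.

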7.1.3 Missing Causal Relationship to Investigational Product for Adverse Events

If the causal relationship to the investigational product is missing for an AE that started on or after the date of the first dose of double-blind investigational product, a causality of yes will be assigned. The imputed values for causal relationship to investigational product will be used for the incidence summary; the values will be shown as missing in the data listings.

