#### 7.4.4 Method of Assigning Subjects to Treatment Groups

Subjects will be enrolled in the study and sequentially assigned an identification number. All subjects will receive active treatment (KRN23); there is only one treatment group in the study.

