#### 7.4.5 Blinding

The study drug will be administered open-label; no study participants will be blinded to study treatment.

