3.2 Blinding and Randomization Methods

All subjects receive KRN23 on an open-label basis. Blinding and randomization are not applicable to this study design.

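### SAP 7.1.3 ties the missing-causality rule to a first double-blind dose that does not exist in this open-label trial; read literally the rule never applies, though the intended start point can be inferred and the likely effect is small

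*SAP*

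**What the plan says.** SAP 7.1.3 covers adverse events whose relationship to study drug was not recorded. If such an event "started on or after the date of the first dose of double-blind investigational product, a causality of yes will be assigned". The next sentence says where the result goes: "The imputed values for causal relationship to investigational product will be used for the incidence summary". The listings keep showing the value as missing.

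The design sections leave no room for a double-blind dose. SAP 3.2: "All subjects receive KRN23 on an open-label basis. Blinding and randomization are not applicable to this study design". Protocol 7.4.5: "The study drug will be administered open-label; no study participants will be blinded to study treatment". Protocol 7.4.4: "All subjects will receive active treatment (KRN23); there is only one treatment group in the study".

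The other adverse event rules start from the first dose without that adjective. SAP 8.8.2: "TEAEs are defined as AEs occurring or worsened in severity on or after the first dose date of IP". SAP 7.1.2, on partial dates, tests the following: "If the month and year match the first dose of IP start date month and year in this study".

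Where no imputation rule applies, SAP 7.1 gives the default: "For all analyses, missing data will be treated as missing, unless otherwise specified". SAP 8.1 repeats that principle.

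**The concern.** The rule in 7.1.3 is a conservative one: when the investigator's assessment is missing, the event counts against the drug. Its trigger, as worded, is a date that exists for no subject. Someone programming strictly from the text would impute nothing. The affected events would remain in the all-TEAE table but would not appear under related TEAEs or serious related TEAEs, both of which SAP 8.8.2 plans at each milestone analysis. That reverses the purpose of the rule, and any resulting error favours the product.

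The protocol does not fill the gap. It has no missing-causality rule of its own, its section 7.6 leaves the handling of missing data to the SAP, and SAP section 1 gives the SAP priority on statistical matters.

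**Working it through.** The plan gives no figure to reproduce. The check is a comparison of texts, followed by one piece of illustrative arithmetic.

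**Step 1: does the trigger date exist?** SAP 7.1.3 needs a first dose of double-blind product. SAP 3.2 and protocol 7.4.4 and 7.4.5 say that all dosing is open-label and that there is one active group. Read literally, the number of subjects with such a date is 0 of 14. (SAP 3.1 states that 14 were enrolled.) Read as the first dose of IP, it is 14 of 14, assuming that every enrolled subject was dosed.

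**Step 2: what happens when the trigger fails?** SAP 7.1 and 8.1 leave the value missing. TEAE status depends on a different date, the first dose of IP (SAP 8.8.2), which every dosed subject has. A post-dose event with missing causality is therefore:

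| Summary in SAP 8.8.2 | 7.1.3 read literally | 7.1.3 read as first dose of IP |
|---|---|---|
| All TEAEs | counted | counted |
| Related TEAEs | not counted | counted |
| Serious related TEAEs (if serious) | not counted | counted |

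**Step 3: direction.** The literal reading only removes events from the related counts and never adds any. It can lower those counts or leave them unchanged.

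**Step 4: what start point does the rest of the SAP use?** Study Day 1 (5.3), partial-date imputation (7.1.2), mapping of unscheduled visits (7.2) and TEAE status (8.8.2) all run from the first dose or first date of IP. Section 7.1.3 is the only exception.

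**Step 5: illustrative size.** The documents give no expected number of missing causality entries, so this step is hypothetical. With a denominator of 14, let k be the number of subjects whose only candidate related event has missing causality. The change in related-TEAE incidence is −k/14:

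- k = 0: no change
- k = 1: 1/14 = 7.1 percentage points lower
- k = 2: 2/14 = 14.3 percentage points lower

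**The case against.** The strongest reply is that no competent reader would treat the rule as void. There is one product, one group and one first dose per subject, so the phrase can point to only one date, and the rest of the SAP uses that date. The second sentence of 7.1.3 describes how imputed values are used, which presupposes that some are imputed. On this view the SAP has one start point with a stray adjective attached. That is persuasive on intent and stands: a programmer would probably apply the rule as meant.

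The documents also make missing causality unlikely. Protocol 8.5.4.1 requires the relationship to study drug for every adverse event. Protocol 8.4.1 has case report forms routinely checked for completeness. SAP 7.1 sends missing data to Data Management for investigation and possible resolution before lock. Any remaining gap would be visible, because SAP 8.8.2 lists all reported events and 7.1.3 shows the value as missing in the listings. This stands too, and it limits the likely size.

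The 7.1-point figure also needs a subject with no other related event. Protocol 5.2.3 reports treatment-related events in 63.6% of subjects in the earlier extension study. If that rate held here (an assumption), 0.636 × 14 = 8.9, so about 9 of 14 subjects would count as related anyway and the overall incidence would not move for them. Counts for individual preferred terms could still change.

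What the reply does not do is make the text correct. A prespecified imputation rule should not depend on a programmer overriding its wording, least of all where the literal reading favours the product.

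**Conclusion.** The wording of SAP 7.1.3 is wrong for this trial and should be corrected, as a minor point. Read literally, the rule applies to no subject, and TEAEs with missing causality are left out of the related and serious related summaries. The word looks like template carry-over, the intended start point can be inferred from the same document, and the practical effect is likely small. It is zero if no causality entry is missing or if the programmer applies the evident intent. The percentage-point figures are hypothetical: they assume the literal reading, a denominator of 14, an unresolved missing entry, and no other related event in that subject. All-TEAE counts and efficacy results are unaffected, and SAP 8.8 plans no hypothesis test on safety data.

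A reader might infer two stronger points that the documents do not support.

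- **That the wording always lowers the related count.** It can lower the count or leave it unchanged, and nothing in the documents shows that any causality entry will be missing.
- **That the rule must also be widened to events that began before the first dose and worsened after it,** because 8.8.2 includes worsening and 7.1.3 speaks only of events that started. That is a separate question from the stray adjective. Protocol 8.5.4.1 already treats a post-consent worsening of a preexisting condition as an adverse event in its own right, so the documents do not show that such events escape the rule.

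**What to change.** In SAP 7.1.3, replace 'first dose of double-blind investigational product' with 'first dose of IP in this study'. This is the start point already used in SAP 7.1.2 and consistent with 5.3, 7.2 and 8.8.2. The rest of the section can stay as it is.

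The cost is one phrase. No data collection, method or hypothesis test changes. Compared with the literal reading, the related and serious related counts can only stay the same or rise. Compared with the evident intent, nothing changes.

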7.1.4 Missing Data in Bone Biopsy Parameter MLt

1. If the MLt data is missing due to low quality of the bone biopsy sample (i.e. no bone biopsy parameters are available for that sample), the MLt parameter is set to missing for the sample. If the MLt data is missing due to very little label uptake because of the mineralization defect (i.e. there is at least one bone biopsy parameter available for that sample), the MLt will be imputed as $O.Th/(MAR*MS/OS)$, where MAR is imputed as $0.3 \mu m/day$, using O.Th, MS and OS from the same visit of the same subject ([Dempster et al. 2013](#)). If any of O.Th, MS or OS at that visit for the subject is missing, MLt will be set as missing.

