**Footnotes to Table 2.1, Table 2.2, and Table 2.3**

-  The Baseline visit should occur no more than 31 days following the Screening visit. The bone biopsy must be completed on a day with no other procedures, and prior to dosing on Day 0. Renal ultrasound, ECHO, ECG, and x-rays may be performed within 3 days of indicated clinic visit to accommodate scheduling availability. The Baseline, Week 48, and Week 96 (or Early Termination; ET) assessments may be completed in any reasonable order (except where indicated) to allow for flexibility in scheduling. However, all Screening/Baseline assessments and inclusion/exclusion criteria must be satisfied prior to dosing.
-  Medical history will include any available previous *PHEX* mutation analysis results for the subject or relevant family members with appropriate X-linked inheritance pattern. Height (in meters) will be obtained using a stadiometer (without shoes).
-  *PHEX* mutation analysis will be performed for all qualified subjects. If the Baseline result for *PHEX* mutation analysis is negative or inconclusive (i.e., No Mutation, Likely Benign, Variant of Uncertain Significance, or Possibly Pathogenic), and informed consent is provided by the subject, reflexive genetic testing will be performed to assess additional genes associated with phenotypes overlapping with XLH. A new blood sample for genetic analysis may be collected if necessary.
-  For patients without prior *PHEX* mutation analysis who fail screening on the basis of the Kainos iFGF23 assay, *PHEX* analysis may be conducted before the baseline visit
-  Available test results related to eligibility will be communicated to the subject within 1 week of the Screening visit by telephone call (TC1). If eligible, tetracycline HCl (or demeclocycline) will be provided to the subject with instructions for administration. The bone biopsy should be performed 5 days after the last dosing day for tetracycline or demeclocycline: The first dose should be given on days -20, -19, and -18 following TC1, and the second dose given on days -8, -7, and -6 following a second telephone call (TC2). The same instructions apply to TC3 and TC4 prior to the Week 48 (or TC5 and TC6 prior to ET if applicable) bone biopsy.
-  Blood and urine to be collected after a minimum overnight fasting time of 8 hours and prior to drug administration (if applicable).

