#### 7.4.6 Treatment Compliance

Trained personnel will administer study drug by SC injection at the investigational site or during home health (HH) visits as indicated in the Schedule of Events for that period (Table 2.1, Table 2.2, Table 2.3). Each administration of study drug will be recorded on the CRF. If a subject does not receive a dose within 21 days of a scheduled dose, that dose should be skipped and the next dose will be administered at the next scheduled dosing visit. Doses should be administered no fewer than 14 days apart.

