5.5 Iliac Crest Bone Biopsy

A bone biopsy of the iliac crest will be performed to assess OV/BV, O.Th, OS/BS, MLt as well as other parameters. Subjects will receive two courses of tetracycline (or demeclocycline) label prior to biopsy associated with the Baseline and Week 48 (or Early Termination if it occurs between the Week 24 and Week 48) visits. Bone biopsy of the trans-iliac crest will be performed by a physician trained and experienced in the procedure. Baseline bone biopsies will be qualitatively analyzed in real time to assess the presence of osteomalacia. If a subject is determined not to have osteomalacia at the time of the initial

biopsy, that subject will continue on study but will not undergo the second bone biopsy at Week 48/ET.

Primary and secondary efficacy endpoints derived from these assessments are provided in Section 8.8.

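### SAP 7.1.4 sorts missing mineralization lag time by which data exist, not by cause, so a biopsy after one missed label course can be imputed as a mineralization defect

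*SAP*

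**What the plan says.** SAP 7.1.4 recognises two reasons for a missing MLt.

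- Poor sample quality, spelled out as the case where "no bone biopsy parameters are available for that sample". MLt then stays missing.
- Low label uptake caused by the mineralization defect, spelled out as the case where "there is at least one bone biopsy parameter available for that sample". MLt is then imputed as O.Th/(MAR × MS/OS), "where MAR is imputed as" 0.3 μm/day, "using O.Th, MS and OS from the same visit of the same subject".

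The section closes with a guard: "If any of O.Th, MS or OS at that visit for the subject is missing, MLt will be set as missing".

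On labelling, SAP 5.5 states: "Subjects will receive two courses of tetracycline (or demeclocycline) label prior to biopsy". Footnote 5 to Protocol Tables 2.1 to 2.3 places the courses on days −20 to −18 and −8 to −6, each after a telephone call, and says that "tetracycline HCl (or demeclocycline) will be provided to the subject with instructions for administration". Protocol 7.4.6 on compliance covers the study drug ("Each administration of study drug will be recorded on the CRF") and has no rule for a missed label course.

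MLt is a secondary endpoint, percent change at Week 48 (SAP 4.3). It is analysed like the primary endpoint: a t-test on change from baseline, or a sign test if normality fails (SAP 8.6.1 and 8.6.3.1). P-values are nominal (SAP 8.1). Six or more biopsy pairs are expected (SAP 3.4).

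**The concern.** The two explanatory clauses in 7.1.4 split samples by whether any biopsy parameter was obtained. That is not the same as splitting them by why MLt is missing. Static measures such as osteoid thickness and osteoid surface come from any adequate core, whatever the subject did with the label. A subject who missed one course, or took it so far off schedule that two separate labels cannot be measured, has an adequate core, no usable distance between labels, and therefore no MAR. The plan has no category for this sample, and by the wording it falls into the mineralization-defect group.

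What is at stake is a wrong MLt value in a very small set of pairs, with nothing in the outputs to show it. The only sensitivity analysis named for biopsy parameters is optional and concerns baseline severity (SAP 8.6.3.1). No analysis without imputed MLt is planned. SAP 7.1.3 keeps imputed causality values out of the listings; 7.1.4 has no similar provision for MLt.

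**Working it through.** The plan states no figure for MLt to reproduce, so the check uses its own formula.

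**Which samples are imputed**

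| Label history | O.Th, OS | MS | MAR | Result under 7.1.4 |
|---|---|---|---|---|
| Both courses taken, little uptake | present | present | missing | imputed, as intended |
| One course missed, single label seen | present | present | missing | imputed, for the wrong reason |
| Both courses missed | present | missing or zero | missing | not imputed: the guard applies, or the formula divides by zero |

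**Size of the error in one subject.** Let O.Th and OS be measured correctly.

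- True MLt = O.Th × OS / (true MAR × true MS)
- Imputed MLt = O.Th × OS / (0.3 × MS seen)
- Ratio R = imputed/true = (true MAR / 0.3) × (true MS / MS seen)

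If true MLt does not change, a miss at baseline gives a false percent change of 100 × (1/R − 1). A miss at Week 48 gives 100 × (R − 1).

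Assumed inputs, not in the documents: true MAR 0.2 to 0.8 μm/day; MS seen with one label 0.5 to 1.0 of true MS. The shift in a 6-pair mean is the subject's value divided by 6.

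| True MAR | MS seen/true | R | Miss at baseline | Shift in 6-pair mean (points) | Miss at Week 48 | Shift in 6-pair mean (points) |
|---|---|---|---|---|---|---|
| 0.2 | 1.0 | 0.67 | +50% | +8.3 | −33% | −5.6 |
| 0.3 | 1.0 | 1.00 | 0% | 0 | 0% | 0 |
| 0.5 | 1.0 | 1.67 | −40% | −6.7 | +67% | +11.1 |
| 0.5 | 0.5 | 3.33 | −70% | −11.7 | +233% | +38.9 |
| 0.8 | 0.5 | 5.33 | −81% | −13.5 | +433% | +72.2 |

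One case in days, with assumed O.Th 40 μm, true MAR 0.6 μm/day, true MS/OS 0.15, and MS halved to 0.075: true MLt = 40/(0.6 × 0.15) = 444 days; imputed MLt = 40/(0.3 × 0.075) = 1,778 days; R = 4.0; false change at baseline (444 − 1,778)/1,778 = −75%.

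**Effect on the tests**

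- Sign test, 6 pairs: turning one non-improver into an improver moves 5 of 6 (two-sided p = 0.219) to 6 of 6 (p = 0.031). A subject who truly improved keeps the same sign when the baseline is inflated.
- t-test, assumed changes of −100, −150, −200, −200, −250 and −300 days: p = 0.001. Inflating one baseline as above moves one −200 to −1,533 (−200 − 1,333); p becomes 0.12, because the spread grows faster than the mean.

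**The case against.** Four points deserve weight.

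- **The guard.** A reader might infer that every missing MLt with some other parameter present is imputed. That describes the classification only. Imputation needs O.Th, MS and OS together, and a subject who missed both courses gets no value. This stands and limits the point to the one-course case.
- **The causal wording.** Section 7.1.4 names the mineralization defect as the cause, so a course known to have been missed arguably falls outside it and under the general rule that missing stays missing (SAP 7.1 and 8.1). But the explanatory clause defines that cause by data availability, and a programmer following it would impute. At the least, two readings are open.
- **Laboratory convention.** The bias needs MS to be reported when only one label is seen. Those conventions are in the Transiliac Crest Bone Biopsy Manual, which is not among the documents. The rule itself largely answers this: it can operate only if MS is reported when MAR is not measurable. How much of the true MS would then be seen remains unknown.
- **Existing controls.** A telephone call precedes each course, concomitant medications are recorded with dates (Protocol 7.5.3.10), and deviations and biopsy parameters are listed (SAP 8.3 and 8.6.3.1). Nothing suggests that missed courses are expected. These controls may supply the facts, but 7.1.4 does not use them.

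**Conclusion.** The point holds as a gap in the sorting rule. A biopsy after one missed or mistimed course can be imputed under a mineralization-defect assumption that does not apply to it. Under the assumed ranges, a miss at baseline gives that subject a false percent change from +50% through 0% to −81%, and a miss at Week 48 reverses the direction. This assumes that a single label yields MS but not MAR.

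Three stronger readings are tempting and not supported.

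- The rule does not systematically favour the drug. A false improvement needs the miss at baseline and true MAR × true MS above 0.3 × MS seen, or the opposite inequality at Week 48.
- It is not shown that one subject decides the MLt result. The test is on absolute change, and an inflated baseline can also weaken the t-test.
- The documents do not equate 0.3 μm/day with severe disease. It is simply the value assigned when uptake is low because of the defect.

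The reach is MLt alone. OV/BV is a static measure and is unaffected. This is a cheap improvement, not a threat to the trial's main conclusion.

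**What to change.** Amend SAP 7.1.4 as follows.

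1. When label records for a biopsy show that a course was missed or mistimed, do not impute; leave MLt missing and list the subject.
2. Impute with 0.3 μm/day only when the missing double label is attributed to the mineralization defect.
3. Flag imputed values in the biopsy listing.
4. Add an MLt analysis without imputed values.

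The trigger should be a recorded miss, not the absence of a complete intake record; otherwise genuine low-uptake samples, for which the rule was written, would be lost through poor record-keeping. MAR and BFR need no matching change, because 7.1.4 uses 0.3 μm/day only inside the MLt formula.

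The cost is a few sentences, use of label-intake records (the concomitant-medication pages may hold them), and one extra table. The statistical downside is possibly one fewer MLt pair. That matters at the minimum size: the smallest two-sided sign-test p is 2 × 0.5^6 = 0.031 with 6 pairs and 2 × 0.5^5 = 0.0625 with 5.
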